Based on the discussion with PMDA, for Japan submission, different endpoints and analysis are specified. The timing of interim, primary and final efficacy analysis is the same with the interim, primary and final analysis of global study.

Primary analysis

Regarding the primary endpoint for Japan submission, the same definition of ORR assessed by IRC will be used as described in Section 5.2.1, but will only include ORR as per RECIST in subjects with solid tumors. ORR according to RANO in subjects with primary CNS tumors is defined as secondary endpoint. Efficacy analysis will be performed for FGFR gene mutation and fusion separately.

The primary analysis will be performed on the pooled data of all tumor histologies that did not meet the futility for the Treated Population in the Broad Panel Cohort as same approach described in section 5.1.3. The futility decision for each tumor type will be made based on the global analysis plan.

The population as the component of estimand is “subjects with advanced solid tumors and target FGFR mutation” for FGFR mutation subgroup and “subjects with advanced solid tumors and target FGFR fusion” for FGFR fusion subgroup. Other components of estimand are the same as Section 5.2.2

The primary endpoint will be calculated with 95% 2-sided exact CI. If the confidence interval excludes 15%, this study will be considered success. Multiplicity will not be adjusted between FGFR mutation and fusion since these are independent and target for different indications. Statistical inference for Core Panel Cohort will not be performed for Japan.

Supplementary analysis

The same supplementary analysis in 5.2.3.2 will be performed for subjects with solid tumors other than primary CNS tumors and will be performed for FGFR mutation and fusion separately.

Major Secondary analysis

For subjects with primary CNS tumors whose ORR is assessed by RANO, the ORR and its 95% 2-sided exact CI will be calculated.

Same as ORR assessed by IIRC, DCR, CBR, DoR and PFS will be analyzed in the same manner with Section 5.3.1, 5.3.2, 5.3.3, 5.3.4 and 5.3.5 except the analysis will be performed for the following subgroups; 1. subjects with FGFR mutation and solid tumors whose ORR is assessed as per RECIST, 2. subjects with FGFR fusion and solid tumors whose ORR is assessed as per RECIST, 3. subjects with FGFR mutation and primary CNS tumors whose ORR is assessed as per RANO, 4. subjects with FGFR fusion and primary CNS tumors whose ORR is assessed as per RANO).

OS will be analyzed in the same manner with Section 5.3.6 except the analysis is performed by FGFR mutation and fusion separately.

Pediatric cohort will be analyzed in the same manner as Broad Panel Cohort.

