Assessment of response will be performed according to Response Evaluation Criteria in Solid Tumors (RECIST, version 1.1) or Response Assessment in Neuro-Oncology (RANO) by the IRC and investigators. Pharmacokinetic assessments (plasma concentrations of erdafitinib and alpha-1-acid glycoproteins, total protein, and fraction unbound, if required, using venous blood samples), biomarker assessments (molecular screening to determine eligibility for the study; and exploratory DNA, RNA, and protein analyses using archival or fresh biopsy tissue and blood (ctDNA) for exploratory research), patients' health-related quality of life (QoL) assessments, and safety assessments (including adverse event [AE] reports and results of vital sign measurements, electrocardiograms [ECGs], physical examinations, clinical laboratory tests, performance status assessment, and ophthalmologic examinations) will be conducted as described on the Schedule of Activities. Additional safety assessments for children and adolescents include radiographic (growth plate assessment and bone age) imaging, DEXA scan for bone densitometry, and clinical laboratory tests for thyroid stimulation hormone (TSH), total triiodothyronine (T3), and free thyroxine (T4) and insulin-like growth factor 1 (IGF-1) will also be conducted as described on the Schedule of Activities in the protocol.

Approximately 280 subjects ≥ 12 years of age with FGFR genetic alterations will be enrolled in the Broad Panel Cohort (approximately 240 subjects for 200 response-evaluable subjects) and Exploratory Cohort (approximately 40 subjects). An additional, approximately 30 subjects will be enrolled in the separate Cholangiocarcinoma Expansion Cohort. The Pediatric Cohort is planned to enroll 20 children or adolescent subjects who had progressed following prior therapies and who had no acceptable standard therapies, and approximately 6 additional children or adolescent subjects who had a newly-diagnosed solid tumor and who had no acceptable standard therapies.

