2.2. Analysis Sets

2.2.1. Efficacy Analysis Set(s)

2.2.1.1. Broad Panel Cohort

The alterations eligible for inclusion in the Broad Panel Cohort consist of target FGFR mutations and any FGFR fusion. The list of Target FGFR mutations eligible for the Broad Panel Cohort is

provided in Protocol Section 10.11. The Broad Panel Cohort will represent the primary cohort of interest for analysis. The efficacy analysis sets of the Broad Panel Cohort are specified below:

- The Treated Population will consist of all subjects (FGFR+) who received at least 1 dose of study drug. The Treated Population is the primary population for analyses of efficacy, baseline demographics and disease characteristics, and patient-reported outcome(s).
- The Response-evaluable Population will include all subjects (FGFR+) who satisfy the following criteria:
 - Met all eligibility criteria for the study;
 - Received at least 1 dose of study drug;
 - Had a baseline and at least 1 adequate post-treatment radiological disease evaluation, or had clinical signs or symptoms of disease progression, or died prior to the first posttreatment disease evaluation (these subjects will be considered non-responders). Adequate disease assessment is defined as having enough evidence to indicate that progression has or has not occurred.

The Response-evaluable Population will be used for the interim analysis, and supplementary efficacy analysis on key endpoints such as ORR and DOR.

- The Core Panel Cohort, which is a subgroup of the Treated Population in the Broad Panel Cohort with a select panel of pre-specified FGFR markers, will be assessed for efficacy as part of the primary analysis. The subset of FGFR markers was selected based on observed clinical activity in previous studies or a high level of recurrence of these alterations across tumor histologies; the subset of FGFR markers is outlined below:
 - FGFR3 mutations: S249C; Y373C; R248C; G370C
 - FGFR2 mutations: C382R
 - FGFR3 fusions: FGFR3-TACC3
 - FGFR2 fusions: FGFR2-BICC1; FGFR2-TACC2

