5. EFFICACY

5.1. Analysis Specifications

The primary analysis for the Broad Panel Cohort will be conducted approximately 6 months after the first dose administration for the last Broad Panel Cohort subject (reaching approximately 200 response-evaluable subjects) and the analysis will be based on Treated Population in the Broad Panel Cohort. At the time of the primary analysis for the Broad Panel Cohort, an analysis of all other cohorts will also be conducted and will include all subjects with the same enrollment cut-off (the date of the last subject enrollment of Broad Panel Cohort) and clinical cut-off as the Broad Panel Cohort. Additional analyses with longer follow-up may be conducted as needed. The final analysis for the Broad Panel Cohort will be performed at the end of the study (per protocol definition).

The Pediatric Cohort will be analyzed separately for efficacy from the Broad Panel Cohort. The final analysis for the Pediatric Cohort will be performed at the end of the study (per protocol definition). The Pediatric Cohort will have the same primary and secondary endpoints as the Broad Panel Cohort. Analysis may also be conducted by pooling subjects from Broad Panel Cohort and Cholangiocarcinoma Expansion Cohort.

The Exploratory Cohort will be analyzed for efficacy based on the Treated Population of the Exploratory Cohort at the time of primary analysis of the Broad Panel Cohort on ORR assessed by investigator.

The Cholangiocarcinoma Expansion Cohort will be evaluated for efficacy at the time of primary analysis and final analysis of the Broad Panel Cohort. Similar endpoints and analyses as Broad Panel Cohort will be conducted for the Cholangiocarcinoma Expansion Cohort.

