5.2. Primary Efficacy Endpoint(s)

5.2.1. ORR assessed by IRC Definition

A subject's best objective response (BOR) is defined as the best objective response a subject achieved during the study in the order of Complete Response (CR), Partial Response (PR), Stable Disease (SD), Progressive Disease (PD), where CR and PR are confirmed as per RECIST v1.1 or RANO. Responders are subjects with BOR of CR or PR. Subjects without measurable disease at baseline or without post-baseline tumor assessment are considered as non-responders.

ORR assessed by IRC is defined as the proportion of responders in an analysis population as assessed by IRC.

For the interim analysis (Interim I, II and III), a subject's BOR may also consider the unconfirmed Complete Response(uCR) and unconfirmed Partial Response(uPR). A subject's response will be classified as unconfirmed CR or PR if only one CR or PR has been observed and a subsequent valid disease evaluation has not been performed yet at the time of the interim analysis. However, a subject will be assigned SD/NE if the subject has only one CR or PR and has no subsequent

disease evaluation and is off study or started subsequent anti-cancer therapy. Two sets of analysis based on different definition of responder will be provided for DRC review for decision making:

- 1) Subjects with unconfirmed response (uCR or uPR) will be considered responders. However, subjects who have initially demonstrated a uCR or uPR but on subsequent evaluation have shown PD will not be considered responders.
- 2) Subjects with unconfirmed response (uCR or uPR) will not be considered as responders.

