In the simulation studies, all selected central molecular screening tumor histologies are assumed for enrollment except pancreatic cancer due to its neglectable FGFR frequency (~0%) based on The Cancer Genome Atlas (TCGA) and Genomics Evidence Neoplasia Information Exchange (GENIE) databases. In addition, the trial allows enrollment of local molecular screening FGFR+ subjects and the tumor histologies that are not limited to the ones listed in [Table A1](#). Thus a group named ‘Other’ is included in the analysis to take in all other tumor histologies not listed in [Table A1](#). Considering the uncertainty of the composition in the group Other, it will not stop early for enrollment for interim futility while the same cap of 30 applies. Final futility assessment will be done on the group Other before being pooled for primary efficacy analysis.

The proportion of each tumor histology for enrollment into the trial is listed in the last column in [Table A1](#). In particular, a 5% proportion is assumed for the group Other. Note that other operational factors such as trial countries, open sites, investigators, etc. are not considered into the prevalence assumption.

Assumptions on Accrual Rate

A peak accrual rate of 5 subjects/week with ramp up is assumed. Ramp up defines periods of simple linear increase in the mean recruitment rate from the start of trial accrual. The mean weekly accrual rate is shown in [Figure A2](#). During simulation, a Poisson process was used to simulate the random arrival of subjects with the specified mean accrual rate.

[figure not shown]

Figure A2: Mean Weekly Accrual Rate Over Time

Parameter Setups

- Sample size: 200 (Response-evaluable Population)
- Cap (Maximum sample size) on each tumor histology: 30
- Three Interim analyses at 60, 100, 140 response-evaluable subjects having completed a specified visit (with 6 weeks to final endpoint)

- Minimum number of subjects required before interim futility stop in a given histology group: 5
- Futility criteria: Less than a 40% chance that $\text{ORR} > 25\%$ (i.e. posterior $\text{Pr}(\text{ORR} > 25\%) < 40\%$)
- Success criteria at the primary analysis: Greater than an 80% chance that $\text{ORR} > 25\%$ (i.e. posterior $\text{Pr}(\text{ORR} > 25\%) > 80\%$)
- Follow-up of enrolled subjects is allowed after tumor histology group stopped enrollment due to futility
- No assumption on dropout

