Mixing nonactive is defined as the proportion of claiming a success (efficacy) in the pooled data at the primary efficacy analysis that is mixed with at least one nonactive histology.

A.3.3. Operating Characteristics Results

20000 simulation runs were conducted to evaluate the operating characteristics of the proposed design.

Selection Power under The Alternative Scenario (Sample Size Determination)

The selection power under the Alternative scenario was used for sample size determination. As mentioned in section 1.4., the sample size of 200 response-evaluable subjects for the Broad Panel Cohort is justified based on extensive simulations with various Bayesian hierarchical model (BHM) designs to achieve approximately 80% power to select at least 80% tumor histologies (e.g., ≥ 12 of 15 tumor histologies) in the Alternative scenario (true ORR at 35% for all histologies). The selection power for Alternative scenario under the proposed design is shown in [Figure A3](#). The probability of selecting more than 12 active histologies for the pooled primary analysis is approximately 83%; the probability of selecting at least 10 active histologies is approximately 95%; the probability of selecting all 15 active histologies groups dropped to 29.4%.

[figure not shown]

Figure A3: Selection Power for Alternative Scenario

Power and Proportion of Success

The power based on pooled efficacy analysis and the proportion of success based on BHM are listed in [Table A3](#) for all scenarios. Note that the proportion of success and the power in the first row of Global Null represent the FWER and FPR and will be discussed the next. The design is achieving above 99% power and proportion of success for scenario Alternative; For scenario Target, it achieves above 95% while has a moderate proportion of success of 70%; The scenario Half-Half Other35 achieves 99% power and 94% proportion of success; The power and proportion of success for the scenario Half-Half Other15 are approximately 98% and 87%; The power and proportion of success for scenario Cholangio35 are lower than 50%, note that if the ORR for Cholangio is 50% with other ORRs remaining the same, the power and proportion of success will increase to approximately 83% and 77% respectively (not listed as one scenario).

Duration of the Trial

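### The SAP's selection power and pooled power are simulated on 200 response-evaluable subjects without dropout, while the pooled primary test uses treated subjects with unassessed subjects as non-responders, and nothing links the two populations

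*SAP*

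**What the plan says.** **Simulated design.** The parameter list in SAP A.2 gives "Sample size: 200 (Response-evaluable Population"), three interims at 60, 100 and 140 response-evaluable subjects, and "No assumption on dropout". The scenarios in A.3.1 set a true ORR of 15%, 25% or 35% without saying whether it applies to treated or evaluable subjects.

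**Planned enrolment.** SAP 1.2 and 1.4 plan "approximately 240 subjects for 200 response-evaluable subjects". SAP 1.4.1 adds that the total may vary with the number of non-evaluable subjects.

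**Planned analysis.** SAP 5.1 states that "the analysis will be based on Treated Population in the Broad Panel Cohort", and 5.2.3.1 applies the one-sided exact binomial test at 0.025 to that population. SAP 5.2.1 states: "Subjects without measurable disease at baseline or without post-baseline tumor assessment are considered as non-responders". A response-evaluable analysis of ORR appears only as an optional sensitivity analysis in 5.2.3.3.

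**Who is response-evaluable.** SAP 2.2.1.1 requires that a subject "Met all eligibility criteria for the study". It keeps subjects with clinical progression and those who "died prior to the first posttreatment disease evaluation (these subjects will be considered non-responders").

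**Printed results.** A.3.3 gives a selection power of about 83% when every histology has a 35% ORR. On pooled power it says "For scenario Target, it achieves above 95% while has a moderate proportion of success of 70"%; Table A3 prints 0.9763 for Target and 1 for Alternative.

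**The concern.** The simulation is the stated reason for choosing 200 evaluable subjects (SAP 1.4.1, Protocol 9.2.1). It follows the population used at the interims but not the one used in the pooled primary test. A treated subject who is never assessed is absent from the simulated data, yet enters the denominator of the primary test as a failure. If the scenario rates are rates in evaluable subjects, as the parameter list implies, the ORR among treated subjects is lower than the simulated ORR.

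At stake are the selection power that supports the sample size and the Target power that enters the alpha comparison in Table A5. No operating characteristics are given for the Treated Population.

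**Working it through.** **Step 1. Size of the gap.** 240 enrolled for 200 evaluable leaves 40/240 = 1/6 not evaluable. If all of these were treated and unassessed, the treated rate would be 5/6 of the evaluable rate: 0.35 x 5/6 = 29.2% and 0.25 x 5/6 = 20.8%. With half that loss (1 in 12), the rates are 0.35 x 11/12 = 32.1% and 0.25 x 11/12 = 22.9%. The documents give no unassessed fraction, so both values are assumptions, and 1 in 6 is the ceiling.

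**Step 2. Reproduce the printed figures.** The A.2 design was re-simulated with the Table A1 prevalences, cap 30, interims at 60/100/140, at least 5 subjects per group, futility if Pr(ORR>25%) < 40%, and the group Other never stopped early. Two inputs are assumptions: the prior on tau-squared read as inverse gamma (0.375, 1.5), and a short accrual ramp. With no dropout:

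- If early-stopped histologies are re-assessed at the end, at least 12 of 15 are selected in 82.7% of runs (printed 83%), at least 10 in 94.6% (printed 95%) and all 15 in 28.8% (printed 29.4%).
- If early-stopped histologies stay out, Target power is 0.973 (printed 0.9763) and the Global Null false positive rate is 18.3% (printed 18.57%). Selection power in this variant is about 68%.

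The 83% matches the design criterion of at least 12. A.3.3 words it as more than 12, which gives 71% here. Under the other reading of the prior, inverse gamma (0.375, 0.75), selection power without dropout was 78-90%, so the results below show size, not exact values.

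**Step 3. Exact check without futility pruning.** The critical value c is the smallest k with P(X >= k | n, 0.15) <= 0.025.

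| n | c | True treated ORR | Power |
|---|---|---|---|
| 200 | 41 | 25% | 0.942 |
| 218 | 44 | 22.9% | 0.851 |
| 240 | 48 | 20.8% | 0.650 |
| 240 | 48 | 29.2% | 0.9995 |

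Here 218 = 200/(11/12), rounded. Pruning removes histologies with poor observed response, so the actual design has more power under Target than this check shows. It gives direction only.

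**Step 4. Full design, scenario rates taken as evaluable-population rates.** Interims are on evaluable subjects, the pooled test is on treated subjects, and unassessed subjects are non-responders. Early-stopped histologies are re-assessed at the end, as SAP 5.2.3.1 describes. Ranges span repeated runs and modelling choices, such as whether the cap of 30 counts treated or evaluable subjects.

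| Unassessed | Final futility step on | Selection power (35%) | Pooled power, Target (25%) | Pooled power, Alternative (35%) |
|---|---|---|---|---|
| none | evaluable | 82-83% | 97-98% | about 100% |
| 1 in 12 | evaluable | 79-82% | about 96% | about 100% |
| 1 in 12 | treated | about 66% | 93-95% | about 100% |
| 1 in 6 | evaluable | 79-82% | 93-95% | about 100% |
| 1 in 6 | treated | 38-43% | 84-86% | about 100% |

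With the final step on treated subjects, selection power is 73% at 5% unassessed and 62% at 10%. If early-stopped histologies stay out, the proper baseline is 68%, and the 1-in-6 treated figure is 34-38%.

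**Step 5. Scenario rates taken as treated-population rates.** With 1 in 6 unassessed, the evaluable rates are 0.35/(5/6) = 42% and 0.25/(5/6) = 30%. Selection power is then 88-90% and Target power 99%, both above the printed values.

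**Step 6. False positive rate.** Under the evaluable reading with 1 in 6 unassessed and the final step on treated subjects, a Global Null of 15% becomes 12.5% in treated subjects, and the rate falls from 18.57% to about 5-6%. Under the treated reading it is about 20-22%.

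**The case against.** The strongest reply is that the figure justifying the sample size may not move at all. Selection is decided by the final futility assessment. SAP 5.2.3.1 does not name its population, applies the interim guideline, and mentions subjects who become evaluable; the interims use response-evaluable subjects. On that reading selection power stays at 79-82%. This stands as one reading. The other is also open, because SAP 3.2 makes this assessment part of the primary analysis, which 5.1 places on the Treated Population, and 2.2.1.1 assigns the response-evaluable set to interim and supplementary use.

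Second, 1 in 6 overstates the loss. The 240 is an enrolment figure, and someone enrolled but never dosed is in neither population. Early deaths and clinical progressions are already among the 200 as non-responders. Treated subjects who failed an eligibility criterion are outside the 200 but can respond. This stands: 1 in 6 is only the end of a range.

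Third, the hypothesis is 35% against 15%, and pooled power at 35% is untouched. Target, at 25%, is the threshold of the Bayesian model. This also stands and confines the pooled-power effect to the Target figure.

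Fourth, the no-dropout setting is disclosed and the printed values reproduce approximately, so there is no arithmetic error. The rationale under Amendment 5 in Protocol 10.14 also says that the adult primary analysis is complete, so restated power would change no enrolment. Both are correct. What remains is how far the stated figures apply to the analysis written in the plan.

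**Conclusion.** The mismatch is in the text and should be corrected: the printed operating characteristics are for 200 evaluable subjects without loss, and the pooled test is on treated subjects. If the scenario rates are evaluable-population rates, Target power is about 93-96% when only the pooled test uses treated subjects, and about 84-95% when the final futility step does too, for losses from 1 in 6 to 1 in 12. Selection power is close to the printed value or well below it, depending on a population the SAP leaves unnamed.

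A reader might infer that selection power is really about 40%, or that the primary analysis has neither stated power. The documents do not support that. It needs evaluable-population rates, the final futility step on treated subjects, and the full 1 in 6 unassessed, all at once. A reader might also infer that the stated power is too high in every case; if the rates are treated-population rates, it is too low.

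The sizes depend on the assumed unassessed fraction and on the assumed prior parametrisation and accrual ramp. The mismatch itself depends on none of these.

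**What to change.** 1. In SAP A.2, state whether the 15%, 25% and 35% rates refer to treated or response-evaluable subjects.
2. In SAP 5.2.3.1, name the population for the final futility assessment.
3. Re-run the simulation with the interims on response-evaluable subjects and the pooled test on treated subjects, counting unassessed subjects as non-responders, over a stated range of unassessed subjects up to 1 in 6.
4. From that run, restate the selection power in SAP 1.4.1, SAP A.3.3 and Protocol 9.2.1, and the power and false positive rate columns of Tables A3 to A5.

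The cost is one re-run of an existing simulation and edits to the two documents. Enrolment and the primary test stay as they are. The drawback for the sponsor is that some stated figures may become less favourable.

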Alternative	0.35	0.35	0.35	0.35	0.35	0.35	0.35	0.35	0.35	0.35	0.35	0.35	0.35	0.35	0.35	0.35
Target	0.25	0.25	0.25	0.25	0.25	0.25	0.25	0.25	0.25	0.25	0.25	0.25	0.25	0.25	0.25	0.25
Half-Half	0.10	0.10	0.10	0.10	0.10	0.10	0.10	0.35	0.35	0.35	0.35	0.35	0.35	0.35	0.35	0.15
Other35																
Half-Half	0.10	0.10	0.10	0.10	0.10	0.10	0.10	0.35	0.35	0.35	0.35	0.35	0.35	0.35	0.35	0.14
Other15																
Cholangio35	0.10	0.10	0.15	0.15	0.35	0.15	0.15	0.15	0.15	0.15	0.15	0.15	0.15	0.15	0.15	0.14

Note: Bold indicates the active (ORR>15%) tumor histologies; no bold represents the nonactive (ORR≤15%).

A.3.2. Definitions of Operating Characteristics

The following terminology will be used to discuss operating characteristics of the BHM analysis.

Selection Power

Selection power is the proportion of simulations that selected at least a given percentage of active tumor histologies (e.g. 80%) to be pooled for the primary efficacy analysis.

Proportion of Success

Proportion of success is the proportion of simulations in which BHM claimed at least one tumor histology as a success. Similarly, the success criteria ($\text{Pr}(\text{ORR} > 25\%) > 80\%$) is used for BHM to claim a success (efficacy) for a given tumor histology.

Family-wise Error Rate (FWER)

FWER represents the proportion of simulations in which BHM claimed false-positive efficacy in one or more of the nonactive tumor histologies. Note that the success criteria ($\text{Pr}(\text{ORR} > 25\%) > 80\%$) is used for BHM to claim a success (efficacy) for a given tumor histology.

The following terminology is used to discuss the exact binomial test in the pooled primary efficacy analysis.

Power

Power is calculated as the proportion of simulations claiming a success (efficacy) on the pooled data of primary efficacy analysis.

False Positive Rate (FPR)

FPR is defined as the proportion of simulations claiming a false-positive success (efficacy) on the pooled data of the primary efficacy analysis. Note that a success is false-positive only when the weighted average of true ORRs is less than 15% for the remaining histologies that didn't meet the futility criteria in the pool for primary efficacy analysis. The weights are the renormalized assumed prevalence in [Table A1](#) for each tumor histology that ended up in the pool.

Mixing Nonactive

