It is shown that the FPR for pooled analysis is around 18.57% for Global Null scenario. Among the false positive cases, there are 16.34% false positive cases that include group Other that did not have interim futility analyses, and 36.7% false positive cases that include at least 1 group with less than 5 subjects. For the Half-Half Other35 scenario, the FPR is controlled at 0.08%. For the Half-Half Other15 scenario, the FPR is controlled at 0.71%. For the Cholangio35 scenario, FPR is at 7.42%. The reasonable FPR control on scenarios Half-Half Other35, Half-Half Other15, and Cholangio35 are aided by the interim and final futility analysis before pooled efficacy analysis, thus helping to prune original tumor agnostic pool with $\text{ORR} < 15\%$ to the final tumor pool with $\text{ORR} > 15\%$ by excluding those tumor histologies that met the futility criteria from final pooling.

Another aspect to consider is the proportion of mixing nonactive tumor histologies for success on pooled data. For the scenarios Half-Half Other35, Half-Half Other15 and Cholangio35, the proportions of mixing nonactive are 19.8%, 23.5%, and 36.1% respectively. Noticing that these scenarios have a considerable number of nonactive tumor histologies, the pooled efficacy analysis may not be performed at the primary analysis if a large amount (e.g. 50%) of tumor histologies were stopped for enrollment.

Note that the FPR for scenario Global Null is inflated as 18.57% and the scenario Alternative is overpowered with power 1, different alpha levels for testing are investigated in [Table A5](#). An alpha level of 0.005 will lower the FPR under 10% while maintaining strong power for both Alternative and Target scenarios. An alpha level of 0.001 will lower the FPR under 5% while moderately sacrificing the power for scenario Target.

Summary

Based on the operating characteristics of different scenarios, the proposed design outlined in this study will have a control of FPR for Half-Half Other35 (0.08%) and Half-Half Other15 (0.71%), and a moderate control of FPR for Cholangio35 at 7.42%, while the FPR for the Global Null is 18.57%. In addition, it achieves a satisfactory performance in terms of testing power (e.g., above 95% power and proportion of success for scenario Alternative) and selection power (approximately 85% power to select at least 80% tumor histologies for scenario Alternative).

Table A3: Operating Characteristics for Duration of the Trial, Ppn of Success, and Power

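### SAP A.3.3 attaches the 83% selection power to more than 12 of 15 histologies; that figure fits at least 12, and the Summary gives about 85% for the same event

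*SAP*

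**What the plan says.** SAP A.3.2 sets the definition: "Selection power is the proportion of simulations that selected at least a given percentage of active tumor histologies (e.g. 80"%). With 15 groups, 80% is 12, so the event is 12 or more. Section 1.4.1 uses this event for the design target of approximately 80% power, and A.3.3 repeats the threshold of 12 or more before giving results. A.3.3 also states why the number matters: "The selection power under the Alternative scenario was used for sample size determination".

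The result sentence under the Alternative scenario then reads "The probability of selecting more than 12 active histologies for the pooled primary analysis is approximately 83"%. Two companion figures follow: "the probability of selecting at least 10 active histologies is approximately 95"%, and "the probability of selecting all 15 active histologies groups dropped to 29.4"%. The Summary at the end of A.3.3 reports "approximately 85% power to select at least 80% tumor histologies for scenario Alternative".

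On precision, "20000 simulation runs were conducted to evaluate the operating characteristics of the proposed design". The set-up in A.2 lists "Sample size: 200 (Response-evaluable Population") and makes no dropout assumption.

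**The concern.** The result sentence changes the event. The definition and the design target concern 12 or more; the reported 83% is attached to 13 or more. The Summary returns to 12 or more but gives a different number for the same design and scenario.

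This figure carries the sample-size justification. A reader who takes the sentence literally will believe that the design selects 13 or more of the 15 active histologies in 83% of trials. A reader who compares the sentence with the Summary cannot tell which number is the simulated result.

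**Working it through.** **Step 1: the SAP's own figures side by side.** Suppose both statements are true as worded: P(13 or more) = 83% and P(12 or more) = 85%. Then

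- P(exactly 12) = 85 - 83 = 2%;
- P(10 or 11) = 95 - 85 = 10%, about 5% each;
- P(13 or 14) = 83 - 29.4 = 53.6%.

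The distribution would dip sharply at exactly 12, and nothing in the design would cause that. If 83% instead belongs to 12 or more, P(10 or 11) = 95 - 83 = 12% and P(12, 13 or 14) = 53.6%, with no dip implied.

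**Step 2: re-simulation of the A.1/A.2 design.** Inputs from the SAP:

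- true ORR 35% in all 15 groups, with Table A1 prevalences;
- total 200, cap 30 per group, no dropout;
- looks at 60, 100 and 140 evaluable subjects, with 6 weeks to the endpoint;
- at least 5 subjects for an interim stop, and stop if Pr(ORR > 25%) < 40%;
- group Other never stopped at an interim;
- the same 40% rule at the final check;
- mu ~ N(-2.19, 2²).

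Two points need assumptions. The accrual ramp length is not in the text; changing it from 2 to 30 weeks moved P(12 or more) only between 81.4% and 81.6%. A.1 puts a mean of 2 on tau², then speaks of the mean for tau. Both readings were run. The tau reading is tau² ~ IG(0.75/2, 0.75 × 2²/2) = IG(0.375, 1.5).

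Two separately written programs (P1, P2) gave, in per cent:

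| Configuration | ≥10 | ≥12 | ≥13 | all 15 |
|---|---|---|---|---|
| SAP A.3.3, as worded | 95 | - | 83 | 29.4 |
| (i) P1: mean on tau, selection by final check only, 20,000 trials | 94.1 | 81.6 | 69.8 | 27.8 |
| (ii) P2: same configuration, 20,000 trials | 95.6 | 84.5 | 73.3 | 31.4 |
| (iii) P2: mean on tau², interim-stopped groups excluded, 12,000 trials | 93.9 | 81.2 | 69.3 | 28.5 |
| (iv) P2: mean on tau², final check only, 12,000 trials | 97.6 | 91.4 | 84.6 | 50.8 |
| (v) P1: mean on tau, groups under 5 subjects exempt at final check | 97.2 | 87.8 | 76.8 | 30.0 |
| (vi) P1: mean on tau, interim-stopped groups excluded | 87.6 | 68.3 | 52.7 | 14.1 |

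The Monte Carlo standard error at 20,000 trials is about 0.3 points.

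Rows (i) to (iii) lie within about 2 points of both companion figures. With a coarser numerical integration, which gave 68-70.5% for 13 or more, they put 12 or more at about 81-85% and 13 or more at about 68-73%. P(exactly 12) is 81.6 - 69.8 = 11.8%, 84.5 - 73.3 = 11.2% and 81.2 - 69.3 = 11.9%, not 2%. Row (iv) does exceed 83% for 13 or more, but it gives 50.8% for all 15 against the SAP's 29.4%. Row (v) comes nearest among the rest and still falls 83 - 76.8 = 6.2 points short. No configuration gives 83% for 13 or more together with 95% and 29.4%.

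**Step 3: size of the overstatement.** 83 - 73 = 10 points to 83 - 68 = 15 points.

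**Step 4: 83% against 85%.** The standard error of the SAP's figure is sqrt(0.83 × 0.17 / 20000) = 0.0027. If both figures are rounded to whole per cents, the closest underlying values are 83.5 and 84.5, a gap of 1 / 0.27, or about 3.8 standard errors. If 85% was rounded to the nearest 5 points, both could come from one result.

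**Step 5: calibration and limits.** Per-histology success probabilities in (ii) are 0.611 (glioblastoma), 0.294 (esophageal) and 0.511 (Other); Table A4 gives 0.608, 0.280 and 0.500. The match is not exact elsewhere. Mean duration is 63-78 weeks against the SAP's 58. Pooled rejection under the Global Null is about 24-25% with the mean on tau and the final check only, and about 14% in (iii), against the SAP's 18.57%.

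**The case against.** The strongest reply is that this is a two-word slip. The correct threshold stands in the same paragraph of A.3.3, no decision rule uses the phrase, and Figure A3, which shows the distribution, could not be seen here. Most of that stands: this is a reporting error, not a design error. It still needs correcting, because the sentence states the result on which the sample size rests.

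A second reply is that 83% and 85% are both given as approximate. That also stands in part. Step 4 is decisive only if both were rounded to whole per cents, and the re-simulated 81-85% is compatible with either figure.

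A third reply is that the prior in A.1 is ambiguous and that one reading reaches 84.6% for 13 or more. That is true, so it cannot be said that no modelling choice gets there. But that reading contradicts the SAP's own 29.4% for all 15.

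A reader might also infer a loss of selection power because no passage names the population for the final futility step, while A.2 simulated response-evaluable subjects without dropout. The documents do not support this. SAP Sections 2.2.1.1, 3.2 and 5.1 lean to the Treated Population. A loss would also require the 35% to hold only among evaluable subjects, and the hypothesis in Section 1.3 has no such limit.

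**Conclusion.** The A.3.3 sentence is wrong as worded. In the configurations close to the SAP's other selection figures, the design delivers about 68-73% for more than 12 of 15 histologies, some 10-15 points below the stated 83%; for at least 12 it delivers about 81-85%. The Summary's 85% leaves a second value for that same quantity.

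It would be tempting to conclude that 200 subjects are too few. They are not: power for at least 12 meets the 80% target in Section 1.4.1. The pooled test keeps power of about 1.00 in the re-simulation, as in Table A3. Nor does the check show that 83% is right and 85% wrong.

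The conclusion rests on an approximate reconstruction of the simulation software's prior and accrual conventions. It is supported by the implausible dip at exactly 12 in the SAP's own figures.

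**What to change.** In the A.3.3 selection-power paragraph, replace *more than 12* with *at least 12*. State one figure for that event in both that paragraph and the Summary, read from the sponsor's simulation output behind Figure A3. Do not drop 85% in favour of 83% without checking that output. Leave the approximate 80% target in Section 1.4.1 as it is.

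The cost is a look-up and a wording correction. Sample size, enrolment, interim timing and analysis are unchanged.

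As an optional clarification, separate from this point, one sentence in SAP Sections 3.2 and 5.2.3.1 could name the population for the final futility step.
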